### 5.4 Agent Administration

#### 5.4.1 Venetoclax

Participants must initiate TLS prophylaxis prior to initiating venetoclax (refer to [Table 5.9.1](#)). Delay initiating Cycle 1 Day 1 dose if the participant is experiencing laboratory TLS (see [Appendix B](#)).

Venetoclax tablets should be taken orally once daily with a meal with water. The tablets should be swallowed whole.

If a participant misses a dose and > 8 hours have passed since the scheduled dose time, the missed dose will be skipped and will not be made up.

Doses that are vomited will not be made up. Doses that are withheld due to toxicity will not be made up.

Participants will be given a Pill Diary to document each dose of venetoclax that is taken or missed ([Appendix G](#)).

Management and dose reductions/delays associated with protocol-therapy related AEs, including TLS are outlined in [Section 6.2](#).

#### 5.4.2 Romidepsin

Romidepsin should be handled in a manner consistent with recommended safe procedures for handling cytotoxic drugs.

Romidepsin must be reconstituted with the supplied diluent and further diluted with 0.9% Sodium Chloride Injection, USP before intravenous infusion.

Each 10 mg single-use vial of romidepsin must be reconstituted with 2mL of the supplied diluent. With a suitable syringe, aseptically withdraw 2 mL from the supplied Diluent vial, and slowly inject it into the romidepsin for injection vial. Swirl the contents of the vial until there are no visible particles in the resulting solution. The reconstituted solution will contain romidepsin 5 mg/mL. The reconstituted romidepsin solution is chemically stable for at least 8 hours at room temperature. However, whenever possible, drug should be prepared within 4 hours of dose administration.

Extract the appropriate amount of romidepsin from the vials to deliver the desired dose, using proper aseptic technique. Before intravenous infusion, further dilute the romidepsin in 500mL 0.9% Sodium Chloride Injection, USP.

Infuse over 4 hours. Patients will receive romidepsin (at a dose of either 14 or 12 mg/m^2 – see [Section 7.2](#) for details) IV on days 1, 8, and 15 of each cycle. On these days it does not matter whether venetoclax is given before or after the romidepsin infusion.

The diluted solution is compatible with polyvinyl chloride (PVC), ethylene vinyl acetate (EVA), polyethylene (PE) infusion bags as well as glass bottles. Romidepsin is stable for 24 hours at room temperature after reconstitution per package insert.

Parenteral drug products should be inspected visually for particulate matter and discoloration before administration, whenever solution and container permit.

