### 5.3 Treatment Plan

Participants will ramp-up daily over the first week of Cycle 1 to the maximum venetoclax dose. From Cycle 1 Days 8-28 and Cycle 2+ Days 1-28, participants will continue at the maximum dose (Figure 5.3) of venetoclax. Romidepsin 14 mg/m^2 will be administered on days 1, 8, and 15 of each cycle.

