### 7.1 General Information

- Baseline values are from screening evaluations.
- For supportive care guidelines see [Section 5.9](#).
- Venetoclax doses missed for toxicity will not be made up.
- Romidepsin doses missed for toxicity will not be made up.
- Permanently **discontinue protocol therapy** if:
  - Participant requires a dose reduction and is already on 100 mg/day of venetoclax
  - Participant requires a dose reduction and is already on 10 mg/m^2 romidepsin
  - Unable to resume treatment within 14 days after last dose of venetoclax
- If the venetoclax dose was reduced during Cycle 1, intra-patient daily re-escalation to steady-state venetoclax dose may be permitted in the absence of a recurrence of the toxicity that led to the reduction following consultation with the Study PI.
- The initiation of a new cycle may be delayed for up to 7 days with written approval from the Study PI in circumstances where the participant is unable to come to the clinic as planned to initiate the new cycle (e.g. planned vacation by participant, lack of transportation etc.).\*

\*If prior approval from the Study PI is obtained, then these modifications will not be considered a protocol deviation. The Study PI will document assessment of the impact of these determinations on the study design, objectives and endpoints or risk to participants. If any modifications to the treatment plan might affect the study design, objectives, and endpoints, or impact the risk of participants, a single subject exception will be sought by the IRB. If the treating investigator is the Study PI, the determination and the rationale for the determination will clearly be documented in the source document(s).

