
Other Grade 4 metabolic laboratory abnormalities
		
 
• Hold the dose until resolution to ≤ Grade 2 or baseline
 
• 1st occurrence 
 
– If resolved within 3 days to resume at the same dose
 
 
 
• If toxicity resolves > 3 days resume at a 50% dose reduction
 
• 2nd occurrence 
 
– If resolves within 3 days to ≤ Grade 2 or baseline, resume at a 50% dose reduction
 
– If toxicity lasts > 3 days permanently discontinue protocol therapy
 
 
 

Hematologic	Romidepsin	Venetoclax

Grade 3 neutropenia <1000 - 500/mm^3
	
 
• 1st occurrence 
 
– Hold until ANC ≥1.5 x 10^9/L
 
– Restart at prior dose
 
 
 
• 2nd occurrence 
 
– Hold until ANC ≥1.5 x 10^9/L
 
– Dose reduce to 12 mg/m^2
 
 
 
	
 
• Hold the dose until ANC ≤ Grade 2 or baseline
 
• Consider using G-CSF
 
• Resume at pre-hold dose
 

Toxicity	Treatment Modification	
Metabolic and nutrition	Romidepsin	Venetoclax
	
 
• 3rd occurrence
 
• Remove from trial
 
	
Grade 4 neutropenia $<500/\text{mm}^3$	
 
• 1st occurrence 
 
– Hold until ANC <math>\geq 1.5 \times 10^9/\text{L}</math>
 
– Restart at prior dose
 
 
 
• 2nd occurrence 
 
– Hold until ANC <math>\geq 1.5 \times 10^9/\text{L}</math>
 
– Dose reduce to <math>12 \text{ mg/m}^2</math>
 
 
 
• 3rd occurrence 
 
– Remove from trial
 
 
 
	
 
• Hold the dose until ANC <math>\leq</math> Grade 2 or baseline
 
• Consider using G-CSF
 
• Consider a 50% dose reduction per investigator discretion
 

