Toxicity	Treatment Modification	
Metabolic and nutrition	Romidepsin	Venetoclax  occurrence and subsequent occurrence, – consider a 50% dose reduction if toxicity resolves within 7 days if toxicity lasts > 7 days, consider permanently discontinuing protocol therapy
Other unspecified Non-hematologic- RELATED	Romidepsin	Venetoclax
$\geq$ Grade 3	
 
• 1st occurrence 
 
– Hold until resolved to <math>\leq</math> Grade 1
 
– then reduce to 12 mg/m^2
 
 
 
• 2nd or 3rd occurrence Grade 3 
 
– Hold until resolved to <math>\leq</math> Grade 1
 
– Dose reduce to 10 mg/m^2
 
 
 
• Any recurrence of Grade 4
 
• Remove from trial therapy
 
	
 
• Hold the dose until <math>\leq</math> Grade 1 or baseline
 
• 1st occurrence, 
 
– resume at same dose if toxicity resolves within 7 days
 
 
 
• consider a 50% dose reduction if toxicity lasts > 7 days 2nd occurrence and subsequent occurrence,
 
– consider a 50% dose reduction if toxicity resolves within 7 days
 
– if toxicity lasts > 7 days, consider permanently discontinuing protocol therapy
 

Other unspecified Non-hematologic- UNRELATED	Romidepsin	Venetoclax
Any Grade	
 
• 1st occurrence 
 
– Maintain protocol therapy for Grades 0-2
 
– Hold until resolved from Grade 3-4 to <math>\leq</math> Grade 1
 
– Dose reduce to 12 mg/m^2
 
 
 
• 2nd or 3rd occurrence Grade 3 
 
– Hold until resolved to <math>\leq</math> Grade 1
 
– Dose reduce to 10 mg/m^2
 
 
 
• Any recurrence of Grade 4 
 
– Remove from trial therapy
 
 
 
	
 
• Maintain protocol therapy
 
• Interruption of protocol therapy is permitted if the investigator consults the Study PI to determine that this is in the best interest of the participant.
 

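### Section 5.4.2 omits the 10 mg/m² romidepsin level used in Sections 7.1 and 7.2, and Section 7 gives conflicting instructions in a few narrower cases

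*Combined protocol and SAP*

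**What the plan says.** Section 5.3 sets the starting dose: "Romidepsin 14 mg/m 2 will be administered on days 1, 8, and 15 of each cycle". Section 5.4.2, which covers preparation and infusion, has patients receive the drug "at a dose of either 14 or 12" mg/m² and sends the reader to Section 7.2.

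Section 7.1 lists the conditions for permanently stopping protocol therapy. One of them is "Participant requires a dose reduction and is already on 10 mg/m 2 romidepsin".

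Section 7.2 gives the reductions by type of toxicity:

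- **Hematologic rows that carry a romidepsin reduction** (Grade 3 neutropenia, Grade 4 neutropenia, Grade 4 febrile neutropenia, Grade 3-4 thrombocytopenia or anemia). First occurrence: hold, then restart at the prior dose. Second: "Dose reduce to 12 mg/m 2". Third: "Remove from trial".
- **Other non-hematologic rows, related and unrelated.** First occurrence at Grade 3 or above: hold, then 12 mg/m². Second or third occurrence at Grade 3: "Dose reduce to 10" mg/m². Any Grade 4 recurrence: off trial therapy.

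**The concern.** The section that staff use to prepare an infusion names two dose levels, and its wording reads as a closed list. On that list nobody could be on 10 mg/m², yet 7.1 makes 10 mg/m² the point at which a further reduction means permanent discontinuation, and 7.2 sends patients there.

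Following the cross-reference settles most of this, but Section 7 does not agree with itself everywhere. Where it does not, two sites could treat identical patients differently: one continues and the other stops for good, or one changes the dose and the other does not. In a two-drug combination whose safety and tolerability is the primary objective of the lead-in, how much drug is given and when therapy ends should not depend on which section a site reads.

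**Working it through.** The plan states no figure to reproduce, so the check sets the sections side by side and counts the reduction steps from 14 mg/m².

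| Place | Levels (mg/m²) | Reduction steps from 14 | Exit |
|---|---|---|---|
| 5.4.2 | 14, 12 | 1 (14→12) | none stated; refers to 7.2 |
| 7.1 | 10 as floor | 2 with the 7.2 levels (14→12→10) | reduction needed when already at 10 |
| 7.2 hematologic | 12 | 1 (14→12) | third occurrence |
| 7.2 non-hematologic | 12, 10 | 2 (14→12→10) | any Grade 4 recurrence |

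**5.4.2 against Section 7.** One step against two. The 10 mg/m² level is missing from 5.4.2.

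**Second Grade 3 non-hematologic event.** The patient is at 12 after the first event. Section 7.2 says hold, then 10, and 7.1 is not triggered because the patient is not yet at 10. Section 7 therefore gives a clear answer.

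**Case (a): third Grade 3 non-hematologic event, patient already at 10.** The same 7.2 entry covers second and third occurrences and calls the action a reduction to 10. The change is 10 − 10 = 0. Section 7.1 says that a patient at 10 who needs a reduction stops permanently. One text keeps the patient on treatment and the other ends it.

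**Case (b): second hematologic event in a patient already reduced for a non-hematologic event.** The hematologic rows say reduce to 12.

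- From 12: 12 − 12 = 0, so no reduction.
- From 10: 12 − 10 = +2 mg/m², or 2/10 = 20% more, which is an increase.

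This takes occurrences as counted within each row, which the table does not state. If they were pooled across rows, one non-hematologic event followed by one hematologic event would still produce an instruction to reduce from 12 to 12.

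**Link to the response endpoint.** Under Section 12.3, a patient who stops before 2 cycles for unacceptable toxicity counts as a non-responder, and one who stops before 2 cycles for a reason other than toxicity, relapse or progression is inevaluable and replaced. Two cycles hold 2 × 3 = 6 planned romidepsin infusions.

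- For the omission in 5.4.2 to matter by this route, a patient needs a first event, recovery, restart at 12, a second Grade 3 event, and a site that disregards the cross-reference, all before the end of cycle 2.
- Case (a) needs three such events with two recoveries in the same window.

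The two-stage design (7 then 18 evaluable patients, at least 4 responses to reject the null hypothesis) uses none of these dose levels.

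**The case against.** The best defense is that 5.4.2 is not where reductions are governed. Its two levels sit in a parenthesis that points to 7.2, and it holds no reduction trigger and no stopping rule. Those are in Section 7, where 7.1 and the non-hematologic rows agree on 10 mg/m² as the lowest level. This largely stands, and it rules out several stronger readings that a reader might infer:

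- **That sites cannot tell when reductions are exhausted.** Section 7.1 states an exit, and 7.2 gives removal triggers by type of toxicity. Most cases with a single type of toxicity are answered.
- **That every patient with a second Grade 3 non-hematologic event is affected.** Section 7.2 answers that case explicitly, and the row covers only toxicities not specified elsewhere in the table.
- **That differing hematologic and non-hematologic ladders are themselves a contradiction.** An exit based on occurrences can coexist with a dose floor. Section 7.1 does not say that every toxicity must pass through 10 mg/m². The plan simply does not say whether the difference is intended.
- **That the response analysis is at risk generally.** The rule in 12.3 on toxicity stops applies only before 2 cycles.

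One could also read the third-occurrence entry as meaning stay at 10, so that no reduction is needed and 7.1 is not triggered. That reading is possible, but the entry itself calls the step a dose reduction, which is the condition in 7.1. The text supports both outcomes. The cross-reference therefore does not cure cases (a) and (b).

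**Conclusion.** The inconsistency is real and should be corrected, but it is narrower than it first looks. Section 5.4.2 omits one romidepsin level that Section 7 uses. Separately, 7.1 and 7.2 conflict for a third Grade 3 non-hematologic event at 10 mg/m², and the hematologic rows of 7.2 instruct a reduction that is not one for patients already at 12 or 10 mg/m².

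What is at stake is exposure and permanent discontinuation. How many patients would be affected cannot be derived, because the documents give no rate for repeated Grade 3 events on the combination. An effect on the response rate through 12.3 is possible only for stops before 2 cycles, and sample size, power and type I error are unchanged.

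The conclusion rests on reading the two levels in 5.4.2 as a complete list and the third-occurrence entry as an instruction to reduce. It takes no view on which dose or stopping rule is right.

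**What to change.** Reconcile 5.4.2, 7.1 and 7.2 so that all three give one consistent set of romidepsin dose levels and consistent discontinuation rules. The revised text should state:

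1. whether the hematologic and non-hematologic ladders are meant to differ;
2. what happens at a third Grade 3 non-hematologic event in a patient already at the lowest level;
3. how mixed toxicities are handled when a patient is already at or below the level named in the row, including whether occurrences are counted within a row or across rows.

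The clinical team decides which levels and rules apply. Adding the missing level to 5.4.2 alone would leave items 2 and 3 open. The cost is an amendment to protocol wording, with no change to the statistical design or sample size.

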#### 5.5 Assessments and Special Monitoring

[Section 10.0](#) summarizes the trial procedures to be performed. It may be necessary to perform study procedures at unscheduled time points if deemed clinically necessary by the investigator.

**Note** the following:

- Review of safety assessments must be performed **within 72 hours prior to the first venetoclax administration (Cycle 1 Day 1)**.
- **Cycle 1 Day 1-6 (venetoclax ramp-up stage):** The **24 hours** post-dose laboratory values must be reviewed prior to the next venetoclax administration.

#### ***Tumor Lysis Syndrome (TLS)***

- There is a potential risk with both venetoclax and romidepsin for TLS in participants with PTCL, especially in those with renal dysfunction and dehydration. In addition, on-target effect of venetoclax could lead to rapid cell death and pose a risk of TLS.
- Patients will be closely monitored for the first 8 days of treatment (Cycle 1, Days 1-8) for signs and symptoms of TLS, laboratory evaluation, and appropriate intervention.
  - Examples of TLS symptoms: fever, chills, tachycardia, nausea, vomiting, diarrhea, diaphoresis, hypotension, muscle aches, weakness, paresthesias, mental status changes, confusion and seizures.
- If any clinical features are observed (see [Appendix B](#)), recheck potassium, phosphorus, uric acid, calcium and creatinine within 1 hour.
- A rapidly rising serum potassium is a medical emergency.
- TLS monitoring during Cycle 1 and prophylaxis are described in [Table 5.9.1](#).

#### **5.6 Duration of Therapy and Criteria for Removal from Protocol Therapy**

Participants will receive protocol therapy until one of the below criteria are met:

- Disease progression
- Completed 26 cycles (~24 months) of protocol therapy
- Participant is deemed intolerant to protocol therapy because of toxicity, despite dose modification/ delay
- General or specific changes in the patient's condition which render the patient unacceptable for further treatment in the judgment of the investigator
- Withdrawal of consent for further protocol therapy (see [Section 16.5](#))

Once participants meet criteria for removal from protocol therapy, the participant should then proceed to End of Treatment assessments. If a patient is still benefiting from treatment at the completion of 26 cycles of therapy, we will consider amending the study to extend the duration of therapy for that particular patient.

Documentation of the reason for discontinuing protocol therapy and the date effective should be made in the source documentation and appropriate eCRF. The COH DCC should be promptly notified of the change in participant status.

#### **5.7 Follow-Up**

Following completion of protocol therapy, all participants will enter follow-up for up to 24 months after ending protocol treatment. This is comprised of:

- **Follow-up for safety**- All participants will be followed until resolution or stabilization of reportable AEs occurring during protocol therapy or starting within 30-days post last dose of protocol therapy. Refer to [Section 7.7](#) for reporting details.
- **Follow-up for response** for those who have yet to have disease progression.
- **Follow-up for survival** - for those who initiated an anti-cancer therapy or have disease progression.

Assessment time points and windows are detailed in [Section 10.0](#).

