**Table 10.0 Study Activity Calendar**

Protocol Activity dd	Screening a	Protocol Therapy b,c							EOT g	Post-last Dose Follow-up (24 months)			
		Cycle 1					Cycle 2 D1 & then weekly	Cycle 3+ D1		Safety 30-days post h	Response i	Survival j	
		D 1 d,e	D 2-7 f	D 8	D 15	D 22							
Informed Consent k	X												
Medical History l	X												
Eligibility m	X												
Registration n	X												
Physical Exam o & Vital signs p	X	X	X	X	X	X	X	X	X	X	X		
Height	X												
ECOG Status (Appx. A)	X	X	X	X	X	X	X	X	X	X	X		
Con-med review q	X	X	X	X	X	X	X	X	X	X	X		
AE Assessment r	X r	-----X s -----											
12-lead EKG	X u												
Pregnancy t	X u												
CBC w/diff, plt & Serum chemistry v	X u	X	X f	X	X	X	X	X	X	X			
TLS serum chemistry monitoring w		X w	X w	X w									
CT/MRI imaging x	X							X y	X g		X		
FDG-PET scan z	X								X				
Bone marrow biopsy/ aspirate	X aa												
Response bb							X y	X			X		
TLS prophylaxis	X cc												
Venetoclax		Orally, daily e,f											
Romidepsin ee		X		X	X		X ee	X ee					
Pill diary ff		X	X	X	X	X	X	X	X				
Tumor tissue	X gg	Optional: During Cycle 1 or 2 hh											
Survival status j												X	

- a. Screening activities to occur within 28 days prior to start of protocol therapy except for [laboratory assessments](#), [bone marrow biopsy/aspirate](#) and [TLS prophylaxis](#).
- b. Protocol therapy may last up to 26 cycles (~ 24 months), until unacceptable toxicity or disease progression (see [Section 5.7](#) for more comprehensive list). If a patient is still benefiting from treatment at the completion of 26 cycles of therapy, we will consider amending the study to extend the duration of therapy for that particular patient.
- c. Each treatment cycle lasts 28 days. The cycle duration does not change, even if venetoclax is held (Note: exceptions due to unusual operational considerations may be permitted; see [Section 6.2](#)).

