- d. Cycle 1 Day 1 is defined as the day of venetoclax and romidepsin initiation. Delay the Cycle 1 Day 1 dose if the participant is experiencing laboratory TLS as defined in [Appendix B](#).
- e. Assessments must be **performed and reviewed within 72 hours prior** to the C1D1 venetoclax dose (except [tumor imaging](#)).
- f. Cycle 1 Day 2-7 ( $\pm$  2 hours) laboratory assessments must be performed and reviewed prior to administration of the Cycle 1 Day 2-7 venetoclax doses.
- g. *End of protocol therapy (EOT) assessments* to be performed no later than 7 days after decision to end treatment (except tumor imaging); assessments performed after last dose of study agent and within 7 days of the decision to end treatment may serve as EOT assessments. **NOTE:** Tumor imaging performed after last dose of study agent and within 28 days of the decision to end treatment may serve as EOT imaging assessment.
- h. *Safety visit* to occur 30 (-2/+7) days post-last dose of protocol therapy. Expedited reporting will occur during this period (See [Section 7.7.2](#)). Safety follow-up may be extended until resolution/stabilization of reportable AEs.
- i. For participants yet to progress, Response Follow-up will occur every 2 months (+/- 7 days) from the day of last response evaluation until progression or the initiation of a new therapy.
- j. Participants who end Response Follow-up will enter Survival Follow-up. Survival assessment to occur bi-annually or as requested by the Study PI via medical record review, review of social security registry, or telephone call.
- k. *Informed consent* process to be fully documented (see [Section 16.4](#)). Informed consent must occur prior to any research only (non-SOC) screening procedures.
- l. *Medical history* to include a review of treatment history, any ongoing medical conditions and medical history pertaining to eligibility on study and involvement during study
- m. *Eligibility criteria* are detailed in [Section 3.0](#).
- n. *Registration* into a COH clinical trial management system (CTMS).
- o. *Standard physical exam* includes weight and skin analysis.
- p. *Vital signs*: heart rate, blood pressure, respiration rate, and temperature.
- q. *Concurrent medications* and reason for administration to be documented from within 10 days prior to protocol therapy up to 30-days-post last dose visit. See [Section 5.9](#) for concomitant medication restrictions and guidelines.

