### 12.1 Statistical Design

This is a multi-institution, single arm Phase 2 trial to evaluate the anti-tumor activity and safety/tolerability of venetoclax with romidepsin in patients with relapsed/refractory mature T-cell lymphoma. Patients will take oral venetoclax daily and romidepsin on days 1, 8, and 15 of each cycle for up to 26 cycles (28-day cycle) Response will be assessed after every 2 cycles until disease relapse/progression. Patients will be followed for 24 months after the end of protocol treatment. The primary endpoint is overall response rate. Secondary endpoints include toxicities, CR rate, duration of response, time to response, PFS, and OS. The study will accrue up to 18 evaluable patients for the primary response endpoint evaluation. The first 6 patients enrolled on the study will be part of a Safety Lead-in to evaluate the safety and tolerability of the proposed dose of venetoclax with romidepsin as described below in [Section 12.1.1](#).

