### **12.2 Accrual and Expected Duration of Trial**

The expected sample size for the Phase 2 response evaluation is 18 patients evaluable for response (assuming the response evaluation passes the first stage). Patients enrolled during the Safety Lead-in of the romidepsin/venetoclax combination will be included in the Phase 2 response evaluation if they are evaluable for response which requires a response evaluation after 2 cycles. We expect that all patient enrolled during safety lead-in will have a response evaluation after 2 cycles. Therefore, the total sample size for the study including the Safety Lead-in is expected to be 18 evaluable patients. Assuming approximately 10% of the patients need to be replaced for safety lead-in or Phase 2 evaluation, the maximum sample size for evaluating the combination of venetoclax and romidepsin is 20 patients.

The 6 patients enrolled on the previous versions of protocols with single agent venetoclax will be analyzed separately and excluded from the main analyses which evaluate the combination of venetoclax and romidepsin. Therefore, the maximum sample size of the study will be 26 accounting for these 6 prior enrollments.

City of Hope saw ~160 PTCL patients per year, with ~30 new patients per year (mix of newly diagnosed and relapsed or refractory). This will be a multicenter study with 3 total sites. We expect a total accrual of 1-2 patients per month across all sites. Therefore, accrual is expected to be completed in 24 months.

Participant duration is planned for 4 years which includes maximum time for treatment (24 months) and expected post-treatment follow-up (24 months). The estimated total study duration will be 6 years, with 2 years of accrual and approximately 4 years of treatment and follow-up for the last patient.

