## 12.5 Statistical Analysis Methods

Patient demographics and baseline disease characteristics, including age, gender, medical history, and prior therapy, will be summarized using descriptive statistics. For continuous variables, descriptive statistics such as number, mean, standard deviation, standard error, median (range) etc. will be provided. For categorical variables, patient counts and percentages will be provided.

Rates and 95% Clopper-Pearson binomial confidence interval (CI) will be calculated for overall response rate (patients that have confirmed CR or PR), as well as for CR rate. Time to response, duration of response (only among subjects achieving CR/PR), overall survival, and progression-free survival will be estimated using the product-limit method of Kaplan- Meier with the Greenwood estimator of standard error. Median progression-free survival and overall survival and their corresponding 95% CIs will be estimated. Observed toxicities will be summarized as summary statistics in terms of type (organ affected or laboratory determination), severity, attribution, time of onset, duration, probable association with the study treatment, and reversibility of outcome.

For the exploratory objective on determining the changes in Bcl-2 gene expression in pre- and post-treatment tumor samples, summary statistics and plots will be used to describe the pre- and post-treatment gene expression levels and the associated change between the timepoints. Paired t-test or Wilcoxon signed rank test will be used to explore the difference in gene expression levels before and after treatment. Data transformation such as log transformation will be considered if appropriate. Exploratory analyses will be performed to investigate the association of the pre-/post-treatment Bcl-2 gene expressions and the change in gene expression with the clinical outcomes. For the exploratory correlation of these gene expression level/change with response, analyses comparing groups of participants defined by response may be conducted by two-sample t-test or Wilcoxon rank sum test. For the exploratory correlation of these endpoints with survival outcomes, survival analysis techniques such as Log rank test will be used. Appropriate regression models will also be considered, such as logistic regression model for

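### Survival follow-up ends 24 months after treatment ends, so from about month 26 OS censoring depends on treatment duration and the Kaplan-Meier tail is unreliable

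*Combined protocol and SAP*

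**What the plan says.** Three places tie the end of follow-up to the end of treatment. Section 5.7 has "Following completion of protocol therapy, all participants will enter follow-up for up to 24 months after ending protocol treatment". Section 12.1 has "Patients will be followed for 24 months after the end of protocol treatment". In Table 10.0 the survival column stands under the heading "Post-last Dose Follow-up (24 months" (closing bracket omitted). Note j to that table describes the method: "Survival assessment to occur bi-annually or as requested by the Study PI via medical record review, review of social security registry, or telephone call". It gives no end date of its own.

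Treatment stops at progression, intolerance, a change in the patient's condition, withdrawal of consent, or the cap in Section 5.6: "Completed 26 cycles (~24 months) of protocol therapy". Section 12.2 adds the two periods: "Participant duration is planned for 4 years which includes maximum time for treatment (24 months) and expected post-treatment follow-up (24 months".

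Table 11.3 counts OS and PFS from the start of protocol treatment. Section 12.5 states that "overall survival, and progression-free survival will be estimated using the product-limit method of Kaplan- Meier", with Greenwood standard errors, and asks for the medians with 95% confidence intervals. It names no survival rate at a fixed time, and it does not mention censoring that depends on treatment duration.

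**The concern.** Kaplan-Meier assumes that patients censored at a given time have the same later mortality as those who stay at risk. Here a survivor's administrative censoring time is fixed by treatment duration, and most reasons for stopping treatment in Section 5.6 are related to prognosis. Survivors who stopped early leave the OS risk set by design while they are still alive. The late curve then describes only those treated longer.

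What is at stake is a named secondary endpoint: the OS curve beyond about month 26, the upper confidence limit of the median, and the median itself if it lies that late. Vital status that is not collected during the study may not be recoverable afterwards.

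**Working it through.** **1. The plan's own figure.** Maximum treatment is 26 cycles × 28 days ÷ 30.4375 = 23.9 months, and 23.9 + 24 = 47.9 months. This reproduces the 48 months (4 years) in Section 12.2. That figure is therefore the sum of two maxima, not a follow-up period common to all patients.

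**2. Censoring time.** Let D be treatment duration in months. The end of follow-up is C = D + 24.
- Stop after 2 cycles (the earliest stop for progression under Section 2.7): D = 2 × 28 ÷ 30.4375 = 1.84, so C = 25.8.
- All 26 cycles: C = 47.9.
- To be at risk at month t, a patient needs D ≥ t − 24: at least 6 months of treatment at t = 30, 12 at t = 36 and 18 at t = 42.

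This step needs no assumption about survival. The change is gradual: in the models of step 4, 37–78% of those at risk at month 26 had been treated for 6 months or more.

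**3. A hand calculation.** The documents give no distribution of OS or treatment duration for this regimen, so these inputs are assumptions. Take 30% responders, exponential OS with medians of 40 months (responders) and 12 months (others), and all non-responders stopping at 3.5 months, so that they are censored at 27.5.
- True S(27.5) = 0.3 × 2^(−27.5/40) + 0.7 × 2^(−27.5/12) = 0.329.
- After month 27.5 only responders are at risk. The Kaplan-Meier limit at month 36 is 0.329 × 2^(−8.5/40) = 0.329 × 0.863 = 0.284.
- True S(36) = 0.3 × 2^(−36/40) + 0.7 × 2^(−36/12) = 0.161 + 0.088 = 0.248. The error is +3.6 points.
- At month 47.5 the limit is 0.329 × 2^(−20/40) = 0.233, against a true value of 0.132 + 0.045 = 0.177. The error is +5.6 points.

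**4. Sensitivity to the assumption.** Large simulations (400,000 patients per scenario, 15 scenarios; median time to progression 2.5–6 months for most patients, median post-progression survival 6–24 months) gave these differences, Kaplan-Meier limit minus true OS, in percentage points:

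| Assumed structure | Month 36 | Month 47.5 |
|---|---|---|
| Same post-progression mortality for all | 0 to +0.6 | −0.1 to +1.1 |
| Shared frailty, or 20% durable responders | +1.3 to +3.9 | +2.8 to +8.5 |
| 25% long-term survivors after progression | −0.5 to −3.1 | −1.8 to −7.5 |
| 15% stop early while in response | −3.5 | −6.8 |

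At month 24 there was no error in any scenario. True median OS lay below month 26 in 12 of the 15, and there the median was essentially unaffected.

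**5. The planned statistic, at n = 18.** The assumed ranges were 22–30% responders, OS medians of 30–60 months in responders and 8–18 in others. The upper 95% limit of median OS was not reached in about 5–85% of simulated trials under the current rule. With common 48-month follow-up it was not reached in about 0.2–40%. With 30% responders and medians of 40 and 12 months, the figures were 38% and 8%. At month 36 only 1.1–2.3 patients remained at risk, of 2.4–6.7 still alive.

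**6. Does common follow-up fit?** The last patient enters at month 24, and 24 + 48 = 72 months, which is the stated 6-year study. Censoring then no longer depends on D, and the Kaplan-Meier limit equals the true curve in every scenario. Across the step 4 scenarios the expected number at risk at month 36, of 18, rises from 0.1–4.1 to 0.5–7.9.

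**The case against.** A reader might infer that the OS curve is biased upward. The documents do not support that. They give no survival data for this regimen, and step 4 shows that the sign follows from the survival structure assumed. Section 5.6 also allows stopping for intolerance or withdrawal, so an early stopper need not have a poor prognosis. A reader might also infer that the curve rests almost only on long-treated patients as soon as month 26 is passed. That is too early: the selection builds up and is complete only by about months 30–36.

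Nor is a 36- or 48-month OS rate a planned output. The plan asks for the median, and in simulated 18-patient trials the median was identical under both follow-up rules in 75–100% of cases. The month-36 difference of 2–4 points is small beside a between-trial standard deviation of 10–15 points. It would also be wrong to extend the point to PFS: patients who stop for progression already have their PFS event, and no PFS error was computed. Finally, note j allows checks at the request of the study PI, so later vital status could be obtained.

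All of this stands, and it limits the point. It does not remove it. The plan also promises the confidence interval of the median, whose upper limit is affected. The permission in note j is optional and sits under a 24-month heading. An error of unknown sign that the plan does not address still leaves the late curve hard to interpret.

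**Conclusion.** The point holds as a potential for informative censoring of OS from about month 26, which the plan does not handle. The dependence on treatment duration follows from the text alone. The size and sign of the error do not. It is plausibly optimistic, by about 2 to 4 points at month 36 and 3 to 8 near month 48, if longer-treated patients have lower later mortality. It is near zero if post-progression mortality is the same for all, and negative if early stoppers do better later. All of these sizes rest on assumed survival and treatment-time distributions.

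The practical effects are a less informative upper limit for median OS and, only if the median lies beyond about month 26, an effect on the median itself. OS to month 24, the primary ORR test and, largely, PFS are untouched. This is a cheap improvement to a secondary endpoint and not a flaw in the main conclusion.

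**What to change.** In Sections 5.7 and 12.1 and in note j of Table 10.0, state that survival status is followed for every participant to a common 48 months from first dose, whatever the date of last treatment. The twice-yearly record, registry or telephone checks already in note j are sufficient. The cost is wording and a few extra status checks for patients who stopped early. No visit or scan is added, and the study length does not change.

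If that is not wanted, state in Section 12.5 that Kaplan-Meier OS and its interval are reported only to 24 months from first dose, the period that scheduled follow-up covers for every patient. This costs nothing to run, but it shortens the reported curve and leaves a later median or upper limit unestimated.
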